In Ukraine, use of ART among people living with HIV (PLWH) has not kept pace with the number of new HIV diagnoses over the past two decades.¹ Of the approximately 250,000 estimated people living with HIV in Ukraine, only 136,105 (44%) are receiving ART.² The majority of those who test positive for HIV never returned to a care provider for a full assessment and enrollment in treatment. The cascade shows significant gaps: about 34,000 PLWH are diagnosed but not on ART. Drop-offs in the HIV care continuum and diminished access to HIV care persist despite scale-up of linkage to care and comprehensive case management programs for PLWH in Ukraine.³⁻⁹ ART use rates are particularly low among HIV-positive people who inject drugs (PWID), with only 38% on ART and 28% virally suppressed.¹⁰ At least 50% of PLWH in Ukraine acquired HIV through intravenous drug use and are likely to be active people who inject drugs (PWID).

Data-to-Care (D2C) is a high-impact public health strategy that integrates multiple sources of data such as clinical data from medical information systems, surveillance data, and ongoing case management assessments with clients to identify PLWH who are not in care, engage them in care, and manage the HIV care continuum.¹¹ D2C strategies complement evidence-based practices for HIV care adherence by integrating clinical and case management data at multiple points along the HIV care continuum, using systematic assessments to identify unmet needs such as substance abuse treatment and make appropriate care referrals, and using data to inform practice change and improve linkage to and retention in care. D2C strategies have been effectively implemented in jurisdictions throughout the United States¹² but are not standard of care in low- and middle-income countries (LMICs) such as Ukraine. How to effectively implement D2C strategies in these new contexts has not been studied. To address this gap, this R34 study will adapt and pilot a D2C strategy to improve HIV care outcomes among not-in-care PWID living with HIV in Ukraine.

This study's Specific Aims are:

- 1) **To adapt a D2C implementation strategy for Ukraine.** We will use the Dynamic Adaptation Process^{13,14} to identify the individual, organizational, policy, and infrastructure factors to adapt an existing US-developed D2C strategy in Ukraine.
- 2) **To study preliminary effectiveness of a D2C strategy versus standard of care** on *primary outcomes* of HIV care engagement, ART initiation or re-initiation, and viral suppression among not-in-care PLWH (n=160); and *secondary outcomes* of engagement or re-engagement in ancillary services (e.g., drug treatment) and quality of life using a cluster randomized trial design.
- 3) **To assess the feasibility, acceptability, and implementation-related processes and outcomes of the D2C strategy** using the Consolidated Framework for Implementation Research adapted for Complex Systems (CFIR-CS)¹⁵ and practice improvement notes, in-depth interviews with D2C implementers and participants, and quantitative D2C usage data.
 - a. Determine the cost of the D2C strategy and estimate the thresholds for the intervention to be cost-effective or cost-saving.

Ukraine is well-positioned as a site to identify how D2C strategies can be implemented in LMICs. With the support of international stakeholders such as PEPFAR and USAID, the Ukrainian Ministry of Health is actively promoting the use of a medical information system (MIS) at the HIV clinic level. The MIS contains patient-level information on HIV care appointments kept, medication prescriptions, all diagnosed co-morbidities, and clinical and laboratory test results.¹⁶ This information can be mobilized

D2C Ukraine

in a D2C strategy that tracks patients through the care continuum, uses data to make decisions about patient care and improve case management practices, attends to psychosocial factors that affect medication adherence (e.g., substance use), and coordinates the provision of non-clinical social services.¹⁷ Our project is positioned to institute and test strategies for maximizing the benefits of this system to improve the HIV cascade for PLWH with history of drug use.

This study addresses 3 NIDA HIV/AIDS research priority areas: developing interventions that influence organizational structure, climate, and culture to promote evidence-based practices; evaluation of adaptation processes and intervention effectiveness in real-world settings; and studies of structural approaches to improve quality and utilization of services. It will be one of the first studies to adapt and evaluate a D2C strategy in an LMIC context, which has implications for HIV policies in Ukraine and globally. The proposed research will increase understanding of the intervention, organizational, provider, and patient characteristics that facilitate successful implementation of a D2C strategy, and the key policy, infrastructure, and process factors necessary to support integration of D2C into existing clinical and case management practices. This study will also position the research team to conduct a larger RCT to determine the effectiveness of a D2C strategy in Ukraine.

[figure not shown]
Background

People living with HIV (PLWH), particularly those who use drugs, experience significant need for supportive services such as case management and substance use treatment.¹⁸

Provision of case management, employment services, housing, and substance use treatment can link and retain HIV positive populations to HIV care and improve HIV related clinical outcomes.¹⁹⁻²⁴ A client-centered approach,²⁵ with the use of a multidisciplinary team²⁶ and coordinated care,^{27,28} is the most effective strategy to providing ancillary services to HIV infected populations. For people who inject drugs (PWID), medication-assisted treatment (MAT) is highly effective in improving linkage and retention in HIV care²⁹⁻³¹ and health outcomes.^{29,32-34} Connecting HIV-positive PWID to ancillary services such as MAT is particularly important in Ukraine, where injection drug use (primarily opiates) accounts for up to 50 percent of new HIV cases.^{17,35,36}

The national HIV care cascade in Ukraine reveals large gaps between the number of people diagnosed with HIV and the number in active care, on ART, and virally suppressed.¹ Among the approximately 250,000

estimated PLWH in Ukraine, only 136,105 (54%) are receiving ART as of 01/01/2020.³⁷ The majority of those who test positive for HIV never returned to a care provider for a full assessment and enrollment in treatment. The cascade (see adjacent figure) shows significant gaps: about 34,000 PLWH are in care but not on ART. The latest national bio-behavioral survey data show that only 52% of PWID are in HIV care, 38% are on ART and 28% are virally suppressed.³⁸

Improving access to and use of clinical and service provision data can lead to better health outcomes for PLWH who are not in care. In the United States, recipients of Ryan White funding increasingly recognize the value of multi-directional information exchanges that use HIV surveillance data, in combination with medical record data, to identify PLWH who are not in care, and intervention opportunities such as referral to HIV specialty care or supportive services.¹¹ A *data-to-care* approach is a public health strategy that integrates multiple sources of data to identify HIV individuals not in care, engage them in care, and manage the HIV care continuum.³⁹⁻⁴¹ A data-to-care (D2C) strategy identifies patterns in services, outcomes, and demographics that might necessitate changes to program activities in order to improve outcomes across the HIV care continuum.⁴² For example, medical information systems (MIS) can be used to track patients through the care continuum and identify points of service breaks. Provider-mediated data usage involves health department staff working with providers to re-engage patients; electronic linkages coordinate between surveillance databases and medical records databases; and in direct outreach, trained staff reach out to persons who are identified as not-in-care through the surveillance system.⁴³

Key features of D2C approaches are collaboration between specialists across multiple public health and health care sectors, and feedback mechanisms to monitor progress and inform practice change. D2C requires cooperation between disease investigators, epidemiologists and researchers, information technologists, and service providers (case managers, clinicians).⁴² Reports can include information on patients' viral suppression, types of prescribed ART, medical visits attended and missed, and engagement in MAT programs for PWID. These reports can then be compared to benchmarks and strategies to realign resources can be developed to respond to

performance gaps, such as more targeted outreach efforts to reach specific populations or more intensive approaches to locating clients who missed appointments.

International and Ukrainian institutions have made significant investments to increase data quality and use to improve HIV outcomes for key populations. The Public Health Center of the Ministry of Health of Ukraine (PHC) in collaboration with the Network of PLWH funded by PEPFAR actively promotes the use of a nationwide Medical Information System (MIS) at the clinic level. The MIS contains patient-level information on HIV care appointments kept, medication prescriptions, all diagnosed co-morbidities, and clinical and laboratory test results. It also includes information on new and previously detected HIV cases. The MIS is also used by NGOs that provide social and medical support for PLWH, allowing for tracking treatment and patient pathways across service sectors and institutions. MIS use has been extended to all regions of Ukraine.¹⁶ PHC created a division to provide support MIS users and developed webinars and other materials to train a wide range of service provider cadre to use the system.¹⁶ PHC is currently working to add new features (such as MAT and hepatitis treatment monitoring) and to expand the use of MIS to facilitate patient tracking and analysis of data on cascade and quality of care indicators at the clinic and oblast (regional) levels.¹⁷ The Ukrainian Institute on Public Health Policy (UIPHP—see Study Team, below) evaluated outcomes of national ART optimization (scale-up of dolutegravir-based regimens) using the MIS data (ART OPTI project). PEPFAR, other international donors, and the PHC recognize the role that effective use of data will play in achieving 90-90-90 targets.

International and Ukrainian institutions have made significant commitments to increasing the quality of HIV/AIDS services, strengthening the capacity of Ukrainian institutions to improve the continuum of HIV services for key populations, and improving access to MAT. USAID and PEPFAR both currently support efforts to improve HIV case finding, primarily through increased HIV testing and initial linkage to care. Moreover, Ukraine has expanded availability of and access to MAT, a critical component of successful retention and care for PWID.^{20-23,44-48} Our proposed D2C strategy complements these efforts and leverages the expansion of MAT in Ukraine by identifying out-of-care HIV-positive PWID and linking them with HIV and other services, including MAT. The D2C intervention would be a valuable amendment that would increase the cost-benefit ratio of any case-management intervention by timely identifying patients who need it most.

A planning grant (R34) is the ideal mechanism for this developmental project. It will allow the research team to establish the feasibility of a D2C for PWID in Ukraine and develop the tools, protocols, and management structure for implementing a full-scale trial. It will also produce important planning information on the cost of implementing a D2C in Ukraine and allow us to determine under what conditions a D2C may be a reasonable investment in Ukraine. Finally, the proposed analytic strategy will inform sample size estimation for a larger trial and determine whether ordinal logistic regression, and more specifically mixed proportional odds models, may be suitable for modeling movement along the HIV care continuum among PWID.

The **scientific premise** of this project is strong. Only 29% of HIV-infected PWID in Ukraine are virally suppressed; of PWID who are on ART, only about 74% are undetectable.⁴⁹ Connecting PLWH who are diagnosed to comprehensive case management and ancillary services can improve outcomes along the HIV care continuum. Clinical and service provision data, including viral suppression, ART prescription, medical visits, and engagement in other services, can be used to improve health outcomes for HIV-positive PWID. This D2C intervention extends current efforts to improve the availability and use of data by assessing clients with standardized, validated assessments on a range

D2C Ukraine

of health and social factors that contribute to engagement in care and using this information to create individualized treatment plans and implement practice change.

INNOVATION

Maximize the utility of new data systems: This project leverages a resource with widespread support from policy makers, funders, and providers. We will institute and test strategies for maximizing the benefits of an MIS to improve the HIV cascade for PWID through data collection, data analysis, and program improvement.

Link clinical and case management data: The proposed D2C strategy prioritizes active review of not-in-care lists and contacting not-in-care individuals to engage them in HIV care and case management. We will develop a mechanism within the MIS to actively monitor and identify individuals who have fallen out of care or at risk for falling out, such as missed visits (which can indicate factors in individuals' lives that may interfere with their ability to remain in care and predict long-term mortality among persons initiating HIV care).^{50,51}

Systematically identify client needs: The proposed data-to-care intervention will integrate an acuity tool into case management. This tool will allow case managers to systematically assess client needs in multiple domains (substance use, mental health, housing, quality of life) over time, develop client-centered treatment plans, and monitor treatment goals tailored to the specific needs of HIV-positive PWID.

Transfer best practices through Implementation Science: D2C strategies are recognized by the Centers for Disease Control and Prevention as a key component of high impact prevention efforts. The WHO recognizes the potential role of digital health information health systems strengthening⁵² and calls for an increase in high-quality research on the integration of health data into health care systems, particularly in low and middle income countries.⁵³ Rigorous Implementation Science research is necessary to guide the adaption of highly complex interventions such as D2C into new contexts, such as LMICs, for maximum effectiveness and sustainability. Our proposed use of the Dynamic Adaptation Process and Consolidated Framework for Implementation Science will yield critical information on the organizational, policy, provider, client, and structural factors necessary for successful D2C implementation.

Project Team and Relevant Experience

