Finalize the d2c strategy The finalization activities will include: (1) refining data extraction protocols and developing a case management module within the MIS; (2) developing a report generation and dissemination protocol for each clinic and (3) specify clinic/implementation team structure, roles, and management plans based on findings from in-depth interviews.

Develop data extraction protocols and create case management module within MIS

The MIS is designed as an electronic medical record system, to be used by clinical providers for routine patient data management. It has centralized architecture, where all data are immediately uploaded to a national-level server. According to the feedback we received in our ART OPTI project, tracking and prioritization of out-of-care patients is one of the most requested features for the MIS. We will partner with the Public Health Center of the MoH, the government body responsible for HIV response and coordination of PEPFAR activities in Ukraine and owner of the MIS to create a module within the MIS that will: a) identify all HIV-positive PWID meeting the criteria of not-in-care [patients registered as HIV-positive who had no HIV medical visits in a calendar year]; b) provide a useful summary of all clinical information that will be needed for case managers [drug use, CD4, viral load, ART history, HIV care appointments made and kept, co-morbid diagnoses and medications, and MAT history]; and c) provide a portal for entry and export of case management data (referrals made, appointments kept, contact attempts, case management notes).

Specific Aim 2: To pilot a randomized clinical trial of a D2C strategy versus standard of care

Study Design

[figure not shown]
This pilot study is designed to test the performance characteristics and capabilities of study design, measures, procedures, recruitment criteria, and operational strategies that are under consideration for use in a prospective RCT. We will also assess feasibility of the RCT by measuring the key parameters for sample size calculation, namely the effect size and coefficient of variation.

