D2C is a structural intervention designed to sustainably change the HIV care providers' practices and facilitate information exchange at the facility level. To address the implementation science questions by measuring the provider-level outcomes and avoid contamination of the control condition due to unblinded allocation of intervention at the patient level, we propose a cluster-randomized trial design for this pilot study and the prospective RCT. We will select eligible HIV clinics (see "Study Sites," above) and randomly assign them 1:1 either to the intervention or the control arms. To achieve greater comparability between the arms, we will match pairs of eligible sites based on organizational context factors derived from Aim 1 data analysis, including facility size and type (e.g., NGO vs. public clinic), service delivery structure (e.g., social workers vs. nurses), and existing services for HIV-positive PWID (e.g. Steps Toward Health) and will randomize within the pairs. This will minimize the degree of between-cluster variation within the groups and increase power and precision.

Randomization will be conducted by the data manager using a computer program.

Sample size

We used methodology from Hayes et al⁸⁴ to determine the effect size that the intervention needs to demonstrate in a feasible matched-pair randomized trial. We assumed the cluster size of 75 patients (based on the optimal case manager workload) with 5 clusters per arm (potentially manageable number given the existing research infrastructure in Ukraine), coefficient of variation between clusters within matched pairs equal to 0.15 (empirically estimated based on the data from 56 clinics in the ART OPTI study, see Previous Studies), power of 80% and 0.05 significance level. Proportion of participants re-engaging into ART within 3 months after inclusion into the study was used as the key outcome. Under the assumptions, the relative difference between the study arms should be at least 22% (e.g. 50% vs 72%). The adjacent chart shows the power and sample size of a pilot trial needed to detect this difference with 0.05 significance level. To achieve 80% power, we will need to recruit 160 participants, or 80 per arm. We propose to divide the sample equally between 4 sites (2 per arm) to test the matching procedures. We do not adjust for loss-to-follow-up because for our main outcomes (ART initiation, viral suppression), loss to follow-up is equal to not achieving the outcome.

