We have powered this pilot study to evaluate feasibility of a prospective cluster RCT. The RCT will be considered feasible if the difference in the proportion of patients achieving the primary outcome (engagement in HIV care) will reach 22% between the study arms. We will estimate the impact of the intervention on the HIV care continuum using mixed effects models. For all outcomes, the data will have the same structure, with observations (t) nested within participants (i) nested within sites (j) nested within matched pairs (k). The correlations among observations will be addressed by using fixed-effects indicators for matched pair and normally distributed random intercepts for sites and for participants. Our mixed-effects models will include indicators for each of the two follow-up assessments, an indicator for site group assignment, and two group-assignment-by-follow-up interaction terms. We will also include sex/gender, age, and baseline covariates that have been identified in preliminary analyses as varying significantly across sites. A logit link function will be used for the primary outcome of ART (re-)initiation (defined above), and the coefficients for the two group-assignment-by-follow-up interaction terms will provide the estimates of the subject-specific intervention effects at 6 and 12 months post-baseline. We will examine the effects of sex/gender, age, substance use severity, ART history at baseline and other covariates in the multivariable models.

We will characterize patterns of behavior that impact HIV transmission (episodes of syringe sharing and episodes of unprotected intercourse in the prior 30 days without viral suppression) and we will use the same mixed-effects approach described above but with a log link function and negative

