We will use the **Consolidated Framework for Implementation Science adapted for complex systems (CFIR-CS)** to guide implementation evaluation of the D2C strategy.^{15,105,106} Key aspects of the D2C intervention are that it covers multiple settings (i.e., patients must access and interact with providers in many different health care sectors), its success depends on interactions and communication between organizations (e.g., between case managers, addiction treatment specialists, and HIV treatment providers); and it uses multiple types and sources of data to identify patterns in services and outcomes that will be used to improve or modify practices. The CFIR-CS organizes implementation factors into 5 domains: **intervention characteristics** (accuracy of data, timeliness of data sharing with partner agencies, development of practice change action plans based on data), **organizational characteristics** (integrating D2C strategy into existing protocols, agency-wide buy-in, commitment to D2C strategy), **providers' roles and characteristics** (case managers' previous experiences, attitude toward the use of data in care provision, relationships with other medical and social service providers, time and resources devoted to providing case management for PLWH), **patients' roles and characteristics** (type of medical and social needs, level of need), and **implementation processes** (participating in the monitoring and practice improvement process, using MIS data to inform practice change). The implementation of the D2C strategy is affected by the **external context** in which these organizations and their staff operate (economic, social, and political factors that may affect implementation process such as MAT "slot" and psychosocial support service).

Measures of implementation are the intermediary outcomes¹⁰⁷ that describe how well the implementation was carried out and include use of the acuity tool with new and returning clients, and use of data generated from acuity tool and MIS to modify practices, documentation of patient visits and contacts. Implementation influences **outcomes**, which include patient outcomes (viral load, appointment kept); provider outcomes (uptake, consistent use, patient contact, outreach efforts, time spent with patients); and processes of care (recruitment rate, extent to which intervention tracks patients and follows up on and coordinates tests, referrals, and care across organizations, settings, and acuity tool domains).

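### The only stated rule for calling the future RCT feasible is an observed 22% outcome difference; recruitment and delivery are measured but have no thresholds and do not enter the decision

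*Combined protocol and SAP*

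**What the plan says.** On purpose, the Background says of the planning grant: "It will allow the research team to establish the feasibility of a D2C for PWID in Ukraine". Study Design under Specific Aim 2 states: "This pilot study is designed to test the performance characteristics and capabilities of study design, measures, procedures, recruitment criteria, and operational strategies". It continues: "We will also assess feasibility of the RCT by measuring the key parameters for sample size calculation, namely the effect size and coefficient of variation". No cut-off is given for the coefficient of variation (CV).

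On the decision, Statistical Analysis and Feasibility Assessment states: "The RCT will be considered feasible if the difference in the proportion of patients achieving the primary outcome (engagement in HIV care) will reach 22" per cent between the arms. Data Collection defines engagement as at least 3 clinical visits spanning at least 6 months in the 12 months after enrolment.

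The 22% comes from Sample size. There the planned RCT is described: "We assumed the cluster size of 75 patients (based on the optimal case manager workload) with 5 clusters per arm", with "coefficient of variation between clusters within matched pairs equal to 0.15" and "power of 80% and 0.05 significance level". The example is 50% against 72%, for re-engagement into ART within 3 months. The pilot itself has 160 participants in 4 sites, 2 per arm.

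On process data, Specific Aim 3a lists among its outcomes "processes of care (recruitment rate, extent to which intervention tracks patients" and follows up on referrals and care. Data-to-Care Usage adds MIS access, contact attempts and attempts needed per participant. None of these has a threshold, and none is tied to the decision on the RCT.

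**The concern.** The pilot is described as a test of whether a larger cluster trial can be run, yet the one rule that turns its results into a decision uses only a difference between arms. That difference is computed among people who have already been found, reached, brought back to the clinic and consented. The stages most likely to limit a larger trial come before that point and cannot move the result.

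A pilot with poor recruitment yield or weak outreach could therefore satisfy the rule, while a well-run pilot could fail to satisfy it through sampling error. A decision on a larger trial would then rest on a noisy estimate from four clinics, while the process data collected for planning carried no formal weight.

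**Working it through.** **1. What the rule can see.**

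| Item | Where it is measured | Threshold | In the RCT decision |
|---|---|---|---|
| Difference in engagement | MIS (Data Collection) | 22% | Yes |
| CV between clusters | Study Design | None | Named as a feasibility parameter, not in the rule |
| Recruitment rate | Specific Aim 3a | None | No |
| Eligible, reached, returned | MIS status codes (Procedures) | None | No |
| Contact attempts, MIS use | Data-to-Care Usage | None | No |
| Acuity-tool use | Specific Aim 3a | None | Only through its effect on the outcome |

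Under First visit, consent follows the return to the clinic. Patients coded ER or ERZ, who are not reached or do not agree to come, never enter the comparison. Of the five steps in Intervention Overview, identification, verification and contact precede enrolment. Only steps 4 and 5 can show in the outcome.

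**2. Reproducing the 22%.** Inputs from Sample size: m = 75 per cluster, 5 clusters per arm, k = 0.15, 80% power, alpha 0.05 (two-sided assumed), p0 = 0.50, p1 = 0.72.

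c = a + (1.960 + 0.842)² × [p0(1−p0)/m + p1(1−p1)/m + k²(p0² + p1²)] / (p1−p0)²

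- Bracket: 0.25/75 + 0.2016/75 + 0.0225 × (0.25 + 0.5184) = 0.00602 + 0.01729 = 0.02331.
- c = a + 7.849 × 0.02331 / 0.0484 = a + 3.78.
- With a = 1, c = 4.78, so 5 per arm. The smallest detectable difference with 5 per arm is 21.4 points, so the plan's figure is reproduced.
- With a = 2 (a larger constant for matched pairs; the plan does not say which it used), c = 5.78, so 6 per arm. The smallest difference with 5 pairs is 25.2 points.

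**3. How often the pilot meets the rule.** I read 22% as percentage points, as in the plan's example, and assume a control rate of 50%. With 2 clinics of 40 per arm:

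SE² = [p0(1−p0)/40 + p1(1−p1)/40 + k²(p0² + p1²)] / 2; P(rule met) = 1 − Φ((0.22 − (p1−p0))/SE)

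| True difference | SE, k = 0 | P, k = 0 | SE, k = 0.15 | P, k = 0.15 |
|---|---|---|---|---|
| 0 | 0.079 | 0.3% | 0.109 | 2.2% |
| 11 points | 0.078 | 8% | 0.114 | 17% |
| 22 points | 0.075 | 50% | 0.120 | 50% |

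Simulation gave the same picture (51% at 22 points with either k). The one-half does not depend on the control rate or on k: an estimate falls above its true value about half the time.

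An observed difference of exactly 22 points has a 95% interval of 7.3 to 36.7 points if clustering is ignored. With k = 0.15 it is 22 ± 1.96 × 12.0, or about −1 to 45 points.

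**4. What recruitment does.** Power of the planned RCT at 50% against 72% with 5 clusters per arm is Φ(√((5−a)(p1−p0)²/bracket) − 1.96).

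| Recruited per clinic | a = 1 | a = 2 |
|---|---|---|
| 75 | 82% | 70% |
| 40 | 74% | 62% |
| 20 | 60% | 48% |

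The number reached per clinic therefore matters to the RCT, and the rule gives it no weight. If the pilot itself stopped short, a chance pass would become likelier. With no effect and k = 0.15, the probability rises from 2.2% at 40 per site to 5.1% at 20 and 10.4% at 10.

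**The case against.** The strongest defence is that the rule uses feasible in a narrow but coherent sense. Sample size derives 22% as the effect detectable in a trial of manageable size, with the cluster size set by case-manager workload. Reaching 22% then means that such a trial would have enough power. Feasibility of D2C as a strategy, which is what the Background sentence concerns, is handled in Aim 3 with broad process measures and interviews. This stands as an account of where the rule came from. It does not supply a criterion for recruitment or delivery, and Study Design says the pilot tests those too.

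Several stronger readings are tempting, and the documents do not support them.

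- *An RCT that cannot deliver D2C would be declared feasible.* It could be, but only if the difference reaches 22%. With no effect that happens 0.3% to 2.2% of the time, so the rule indirectly catches gross failure after enrolment.
- *A smaller difference means the RCT is infeasible.* The text says if, not only if. It leaves that case undefined.
- *Recruitment and delivery are ignored.* They are measured. What is missing is a threshold and a link to the decision.
- *75 per clinic is out of reach because the pilot takes 40 per site and sites need only 150 registered patients.* The 40 is an allocation (160/4), not a ceiling. The 150 is a minimum for site selection, not the pool of eligible patients. Neither shows what a clinic can recruit.
- *The status codes record enrolment.* The E(R)S code is assigned at the visit, before consent. Consent has to come from study records.
- *Feasibility is the pilot's one product.* It also covers adaptation, preliminary effectiveness, cost and sample-size inputs.

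It is also fair to say that loss of survey follow-up does not threaten an RCT on the primary outcomes, which come from the MIS.

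**Conclusion.** The concern holds in a limited form. The plan has one stated rule for RCT feasibility, and it can misclassify in both directions. It cannot detect poor yield or weak outreach before enrolment. It is also met only about half the time when the full assumed effect is real, and 8% to 17% of the time at half that effect. It does give reasonable indirect protection against complete failure of delivery after enrolment.

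These figures rest on reading 22% as percentage points, a normal approximation with only four clinics, a CV of 0.15 where clustering is included, and a 50% control rate. That rate comes from an example about ART re-engagement at 3 months, whereas the rule is applied to engagement over 12 months. The documents give no control rate for engagement. The result of about one half does not depend on that rate.

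**What to change.** In Statistical Analysis and Feasibility Assessment, stop defining feasibility by the observed 22% difference. Report that difference with its confidence interval, together with the CV, as input to the RCT sample size. Before outcome data are seen, add progression thresholds chosen and justified by the sponsor:

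- **Recruitment.** For each site, report the eligible-to-reached-to-returned yield from the MIS status codes, and the consented and enrolled count from study records. Give these by arm, because outreach effort differs by design. Compare the projected number per clinic with the 75 assumed in Sample size, over an RCT recruitment period that must be stated; the documents give none.
- **Delivery.** Set a minimum share of intervention participants with their scheduled acuity assessments recorded. First reconcile the schedule: Intervention Procedures has clients assessed every 3 months, while the Acuity Scale Levels table gives 6-monthly reassessment at Level 1. The Aim 3 data analysis also refers to seven D2C steps where Intervention Overview lists five; reconcile these before counting delivery by step.
- **Survey completion**, as a secondary criterion only.

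Also state what follows if some thresholds are met and others are not.

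The cost is protocol wording and simple counts from data already collected. The downside is that the sponsor must commit to thresholds, and the RCT could be judged not feasible despite a favourable outcome difference.
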